## 7.2 Laboratory Evaluations

The following laboratory parameters will be summarized and displayed at the scheduled time points:

- **Biochemistry:** total bilirubin, alkaline phosphatase, gamma-glutamyltransferase, AST, ALT, lactate dehydrogenase, creatinine, urea, total protein, albumin, glucose, inorganic phosphate, sodium, potassium, calcium, and chloride. In the extended clinical laboratory analysis, fasting serum lipids will be included as well (i.e. total cholesterol, HDL-cholesterol, LDL-cholesterol, LDL/HDL cholesterol ratio (calculated as LDL/HDL) and triglycerides)
- **Hematology:** leukocytes, erythrocytes, hemoglobin, hematocrit, thrombocytes, partial automated differentiation (lymphocytes, monocytes, eosinophils, basophils, neutrophils and neutrophils segmented), mean corpuscular volume, mean corpuscular hemoglobin, and mean corpuscular hemoglobin concentration.
- **Acute phase proteins:** fibrinogen, CRP, and ESR.
- **Urinalysis:** erythrocytes/blood, urobilinogen, ketones, glucose, protein, pH, and leukocytes.
- **Coagulation:** activated partial prothrombin time, prothrombin time, and INR (the latter for subjects on warfarin only).

For lab tests with numeric values, tables showing descriptive statistics (mean, median, standard error, minimum, and maximum) per lab test category (hematology, biochemistry, acute phase proteins, urinalysis, coagulation), lab test and unit and time point by treatment group and using the safety population will be prepared for:

- actual values
- absolute changes from baseline (definition in section 4.2.1)

Urinalysis results will be presented in a frequency table per lab test and time point.

The statistical summary will only present results in Standard International (SI) units. Other units will not be presented. In the tables, the number of significant digits of the original values will be used to determine the number of decimals that will be printed.

All values will be compared to their matching normal ranges (low, normal, high). For both values and normal ranges the SI units will be considered to determine abnormalities. Additionally, for key hematology and biochemistry parameters, toxicities will be derived according to the common terminology criteria for adverse events (CTCAE, see appendix 16.2) grading, version 4.03 (ALT, AST, total bilirubin, gamma-glutamyltransferase, leukocytes, neutrophils, thrombocytes, fibrinogen and cholesterol). Details for derivation of classification based on normal ranges of laboratory parameters can be found in section 12.4.2.

Cross-tabulations per lab test category (hematology, biochemistry, acute phase proteins, urinalysis, coagulation), lab test and time point will show the shift at each post-baseline time point versus the baseline.

The following types of cross-tabulations will be prepared:

- for all tests with normal ranges: shift in abnormality (L/N/H)
- for ALT, AST, total bilirubin, GGT, leukocytes, neutrophils, thrombocytes, fibrinogen and lipids test results only: shift in CTCAE toxicity grades (grade 1 to 4)

Longitudinal box plots will be prepared for the following variables: neutrophils, platelets, ALT, AST and LDL/HDL ratio.

A detailed list of tables, figures and listings can be found in section 13.4, section 14 and section 15.4, respectively.

### 7.3 Physical Examination

Abnormal physical examination findings will be listed (see section 15.4). No summaries will be provided.

### 7.4 Vital Signs

The following parameters will be analysed: weight, systolic and diastolic blood pressure, pulse rate and body temperature.

Tables showing descriptive statistics (mean, median, standard error, minimum, and maximum) per vital sign test and unit and time point by treatment group and using the safety population will be prepared for:

- actual values
- absolute change from baseline

A detailed list of tables and listings can be found in section 13.4 and section 15.4, respectively.

## 8 ANALYSIS OF PHARMACOKINETICS

All analyses will be run on the PK population.

Drug concentration will be analyzed descriptively (n, arithmetic mean, SD and SE, median, minimum and maximum, 5% and 95% percentiles, CV% of arithmetic mean, geometric mean and geometric SD) by treatment group and timepoint.

Individual pharmacokinetic concentrations will be reported in  $\mu\text{g/mL}$ . Concentrations in  $\text{ng/mL}$  will be converted. Values BQL will be handled as detailed in section 4.3.2.

Pharmacokinetic concentrations and descriptive statistics will be reported to 3 significant digits for values up to, but not including 1000. Values equal to and above 1000 will be reported as the value without decimal signs. In case the actual sampling time deviates more than allowed per study protocol from the nominal time, these samples will not be included in the calculation of descriptive statistics.

A detailed list of tables and listings can be found in section 13.3 and section 15.4, respectively.

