3.4.1.2. TREATMENT AND ASSESSMENT PERIOD

Week 0 (Baseline)

As the Baseline Visit (Week 0) coincides with the Week 24 (Study ALX0061-C201) or Week 12 (Study ALX0061-C202) visit of the preceding study, assessments planned at both visits only need to be performed once (results will be used for both studies). The data collected at the Week 24/Week 12 visit of the preceding study will be used for the statistical analysis based on all necessary parameters assessed at the Baseline Visit (Week 24/Week 12).

Post-baseline Assessments

Eligible subjects will receive treatment q2w from Week 0 up to and including Week 102. Subjects will return for 11 ambulatory post-baseline visits planned during the treatment and assessment period on Weeks 4, 8, 12, 24, 36, 48, 60, 72, 84, 96, and 104.

An End of Treatment Visit (or Early Termination Visit) will be performed at Week 104 (or within 2 weeks after the last visit for subjects who discontinue early) and a Follow-up Visit will be performed 12 weeks after the last study drug administration. Note that subjects who withdrew for reasons of lost to follow-up, informed consent withdrawal, or death, will not have any follow-up assessments.

All assessments will be performed at the visits as indicated in the [Schedule of Assessments](#).

All post-baseline visits, except for the Early Termination Visit, may occur at the indicated week \pm 3 days throughout the study versus the date of the Baseline Visit.

Any subject with < 20% improvement from baseline (of the respective initial Phase IIb study) in both swollen and tender joint count (SJC and TJC; 66/68 counts) at any of the visits at Week 12, 24, 36, 48, 60, 72, 84, or 96, will discontinue from the trial.

Missed visits:

- If a subject misses a visit but a new visit can be performed within 1 week of the originally planned missed visit (i.e., within 3 weeks of the previous dosing [including dosing in the respective initial Phase IIb study]), then all assessments per missed visit should be performed at this new visit and the study staff should administer the study drug to the subject and maintain the subject's original injection schedule. In case of rescheduling of missed visits, total duration of the assessment period should remain 104 weeks.
- If a subject misses a visit and the visit can only be performed later than 3 weeks of the previous dosing, the site should contact the CRO.

Missed self-administration date:

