- If a subject misses a self-administration time point a new injection should be performed as soon as the patient remembers and within 1 week of the planned missed self-administration time point. If later than 1 week of the missed self-administration time point, then the CRO should be contacted. In case of rescheduling of missed visits, the total duration of the assessment period should remain 104 weeks.

If a subject misses a dose of MTX on their regularly scheduled dosing date, they should take the forgotten dose as soon as they remember; however, if more than 72 hours have elapsed since the missed dose, the subject should contact the Investigator for further dosing instructions.

For all subjects, injections should not occur less than 1 week apart. The CRO/Sponsor should be contacted if this cannot be respected. In case of interruption of more than 2 consecutive administrations, the subject should be discontinued from the study.

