3.6.5. EVALUATION OF PHARMACOKINETIC PARAMETERS

The procedures for obtaining ALX-0061 serum concentrations are found in section [3.4.2](#).

Evaluation of Pharmacokinetics

PK analysis will be performed on the PK population.

Individual study drug concentrations will be listed. In addition a listing of the actual sampling times relative to the study drug administration times will be presented.

Study drug concentrations will be summarized by scheduled sampling time.

Pharmacokinetic Model

ALX-0061 serum concentrations obtained from all subjects in the study will be pooled together with available data collected so far in previous studies. A population PK analysis will be conducted to describe the population mean and variability of ALX-0061 exposure in the study population based on pharmacostatistical nonlinear mixed effect models.

PK modelling will be performed under the responsibility of Ablynx NV. Results will be provided in a separate Modelling and Simulation report.

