**Listing 16.2.4.2: PK: Sampling times**

Listing of nominal sampling times, actual sampling times and sampling time deviations. In case the actual sampling time deviates more than allowed per study protocol from the nominal time, the time point will be flagged.

Population: PK population.

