A. All assessments are to be completed prior to the study drug administration, except for subjects who discontinue study drug injections. The order of assessments if more than 1 assessment is planned at the same time should be performed according to the following principles: vital signs should be assessed prior to blood sampling; patient reported outcomes should occur prior to the physician's joint evaluation, independent joint assessment should occur prior to physician's global assessment, and study drug should be dosed after all other assessments have been performed.

B. The Baseline Visit will coincide with the 24-week End of Treatment Visit of the preceding Study ALX0061-C201, or with the 12-week End of Treatment Visit of Study ALX0061-C202. The results from the End of Treatment Visit assessments for these studies do not have to be repeated at baseline for this study, and include physical examination, vital signs, TB evaluation (questioning), routine/extended clinical laboratory analyses (at Week 22 in Study ALX0061-C201 or at Week 10 in Study ALX0061-C202), pregnancy test (urine), morning stiffness duration, joint assessment (66/68-joint count), patient pain VAS, HAQ-DI, SF-36, FACIT-F, physician and patient global assessment, concomitant medication, AEs, PK blood samples, and immunogenicity.

C. The Early Termination Visit is to be performed 2 weeks after the last study drug dosing for subjects who discontinue from the trial for other reasons than described in the efficacy discontinuation criteria (see section 3.2.3.2), unless they discontinue during a study visit, in which case that becomes their Early Termination Visit. For subjects who will meet the efficacy discontinuation criteria at Week 12, 24, 36, 48, 60, 72, 84 or 96, the visit at which subjects will meet these discontinuation criteria is defined as the Early Termination Visit.

D. All post baseline visits may occur at the indicated week ± 3 days throughout the trial.

E. At the study visits at Weeks 0, 4, 8, 12, 24, 36, 48, 60, 72, 84, and 96, study drug is to be administered s.c. at the study site. At all other time points, subjects are allowed to self-administer away from the clinic. Subjects unable to have injections administered away from the study site will be required to return to the site every 2 weeks for administration of study drug by an authorized health professional.

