f. Vital signs (assessment after 5 minutes in supine position) will include weight, blood pressure, pulse, and temperature. A height measurement is not required (data available from the preceding study). In case blood sampling is to be performed at the same visit, the vital signs assessment is to be performed prior to the blood sampling.

g. If TB is suspected at any time during the study, chest x-ray and interferon-gamma release assay (IGRA) should be performed.

h. Samples for routine clinical laboratory analyses will be collected predose, and include blood chemistry, hematology, acute phase proteins (C-reactive protein [CRP], erythrocyte sedimentation rate [ESR], fibrinogen) and urinalysis (urinalysis at Weeks 48 and 104). For subjects on warfarin, international normalized ratio (INR) will be performed at Weeks 0, 4, 8, 12, 24, 36, 48, 60, 72, 84, and 96, or at the Early Termination Visit.

i. At the indicated visits, samples for extended clinical laboratory analyses, including fasting serum lipids on top of the routine clinical laboratory analyses, will be performed predose. Extended clinical laboratory samples will be taken predose after the subject has been fasting for at least 10 h.

j. AEs will be recorded from the time the informed consent form is signed through the Follow-up Visit. The Investigator must follow-up on all SAEs and AEs until the events have subsided, returned to baseline, or the subject's condition has stabilized in cases of permanent impairment. In case of acute or delayed severe/serious hypersensitivity reactions, an additional serum sample should be collected as soon as possible after the start of the event (blood volume: 5 mL).

k. PK and immunogenicity samples will be taken predose.

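### SAP section 8 screens PK samples against an undefined nominal time, not days since the last injection, so samples far from the 14-day interval stay in the concentration summary

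*SAP*

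**What the plan says.** SAP section 8 summarises concentrations by treatment group and time point. Its only timing rule, which governs what enters the summary statistics, reads: "In case the actual sampling time deviates more than allowed per study protocol from the nominal time, these samples will not be included". The SAP does not define nominal time. An allowance could be sought in three places:

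- **Visit window.** SAP Appendix 1, footnote D: "All post baseline visits may occur at the indicated week ± 3 days throughout the trial". Protocol 3.4.1.2 gives the same tolerance, counts it from the Baseline Visit date and exempts the Early Termination Visit.
- **Rescheduling.** Protocol 3.4.1.2 lets a missed visit, with all its assessments, be made up within 1 week of the planned date and within 3 weeks of the previous dose.
- **Position relative to the dose.** SAP Appendix 1, footnote K: "PK and immunogenicity samples will be taken predose". Protocol 3.4.7 places predose samples between waking and dosing.

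On dosing, Protocol 3.3.4 allows self-administration at every time point except Weeks 0, 4, 8, 12, 24, 36, 48, 60, 72, 84 and 96. Under Protocol 3.4.1.2 a missed home injection should be given "within 1 week of the planned missed self-administration time point", and injections should not be less than 1 week apart.

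On listings, Protocol 3.6.5 states that "a listing of the actual sampling times relative to the study drug administration times will be presented". SAP Listing 16.2.4.2 is described as "Listing of nominal sampling times, actual sampling times and sampling time deviations", with a flag for samples outside the allowance. SAP section 11 declares four changes from the protocol, none about PK.

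**The concern.** A predose concentration under two-weekly dosing is interpretable only if one knows how long ago the last injection was. The SAP rule does not look at that interval. Table 14.2.6.1 and the mean-concentration plots (Figures 14.2.1.13.1 and 14.2.1.13.2) could therefore combine levels from clearly different points after dosing under one visit label.

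Over two years of dosing that may be largely at home, a drift in the plotted means could reflect changing punctuality as well as changing clearance or anti-drug antibodies. Protocol 3.3.6 relies on serum concentrations to confirm compliance, while the compliance measure in SAP 12.2.1 counts doses and does not register late ones. Without the interval beside each concentration, a reader cannot easily separate these explanations.

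**Working it through.** The plan gives no figure on this point, so there is none to reproduce. The check uses the plan's dates and the protocol's half-life.

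**1. Which dose precedes each PK sample?** SAP 3.3 lists post-baseline PK samples at Weeks 12, 24, 36, 48, 60, 72, 84, 96 and 104. The doses two weeks before fall at Weeks 10, 22, 34, 46, 58, 70, 82, 94 and 102. None is among the site-administered weeks, so each may be given at home.

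**2. What intervals can arise?** Days since last injection = 14 + v − d, where v is the shift of the visit and d the delay of the preceding injection.
- Visit on date (v = 0), dose 7 days late (d = 7): 14 + 0 − 7 = 7 days. The two injections are then exactly 1 week apart, which is permitted.
- Visit on date, preceding dose missed: 28 days. Protocol 3.2.3.2 discontinues for 2 consecutive doses and Protocol 3.4.1.2 for more than 2. Those statements need reconciling, but one missed dose meets neither.

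**3. Does the rule remove them?** If nominal time is the planned visit date, the deviation is zero. If it means only predose, both samples are predose. Both are kept either way. The 3-week limit in Protocol 3.4.1.2 governs made-up visits, so it does not apply to a visit on its date. The windows in SAP 12.1.1 do not help: Week 24 spans days 141 to 197 around target day 169, and the only dose-based cut is more than 28 days after the last dose of treatment.

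**4. How different are the levels?** Assume linear superposition with instantaneous input and half-life h. Let r = 2^(−14/h); the steady-state trough in dose units is T = r/(1 − r).
- Dose d days late, sampled s days later, relative to T: (T·2^(−d/h) + 1)·2^(−s/h)/T.
- Last dose missed, relative to T: 2^(−14/h).

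With h = 15 (Protocol 1.2.4.1), r = 0.524 and T = 1.099:
- 7 days late, sampled at 7 days: (1.099 × 0.724 + 1) × 0.724/1.099 = 1.18
- missed dose, sampled at 28 days: 0.52
- ratio between the two: 1.18/0.52, about 2.3

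The 15 days comes from the linear clearance term alone, and the protocol describes faster, concentration-dependent clearance at lower levels. With an assumed h = 7, r = 0.25 and T = 0.333, and the two values become 1.75 and 0.25.

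**5. Can 14-day samples be lost?** If dose and visit are both 5 days late, the interval is 14 + 5 − 5 = 14 days. At h = 15 the level is (1.099 × 0.794 + 1) × 0.524/1.099 = 0.89, closer to the reference than either sample in step 4. The same interval arises when both are 4, 6 or 7 days late.

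| Reading of the protocol allowance | Outcome for this sample |
|---|---|
| ±3-day visit window only | dropped |
| visit window plus 1-week rescheduling | kept |
| predose only | kept |

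**6. Listing.** Protocol 3.6.5 asks for sampling times relative to dosing times. Listing 16.2.4.2 names nominal times, actual times and deviations, so the dose-relative time is not among its stated contents.

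**The case against.** A reader might infer that the rule discards valid 14-day troughs. The documents do not establish that. The ±3-day window is not the only numerical allowance: Protocol 3.4.1.2 also permits a missed visit to be made up within 1 week, and on that reading, or if nominal means predose, the sample stays. The loss is conditional.

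A reader might also infer that the SAP presents these levels as troughs. It does not use that word for the table or figures. It summarises by scheduled sampling time, as Protocol 3.6.5 asks, so the summary itself is no undeclared change.

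Other points carry weight. At h = 15, a 14 ± 3-day window would keep an 11-day sample at 2^(3/15) = 1.15 and a 17-day sample at 0.87, so the late-dose value of 1.18 is only slightly outside that range. The larger departure needs a missed dose, which is recorded in the eCRF and visible in Listing 16.2.2.4. Self-injection is permitted, not required. Population PK is modelled and reported separately, and no efficacy or safety conclusion rests on Table 14.2.6.1.

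These points limit the importance of the finding. They do not supply a rule on time since dose, a definition of nominal time, or the dose-relative listing.

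**Conclusion.** The point holds in limited form. Under either reading of nominal time, samples taken on the planned date but about 7 to 28 days after dosing enter the descriptive PK summaries together, at about 1.18 to 0.52 times the 14-day trough. That range assumes a 15-day half-life, linear kinetics, instantaneous input and steady state beforehand; faster clearance at low concentrations would widen it. Frequency cannot be derived from the documents. Loss of 14-day samples from rescheduled visits follows only if the allowance is the ±3-day window alone. The listing in SAP 15.3 does not name what Protocol 3.6.5 requires, and section 11 does not declare the difference. The consequence is limited to descriptive PK output, but the correction is cheap enough to be worth making before database lock.

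**What to change.** In SAP section 8, define nominal time and state which protocol allowance applies. For post-baseline on-treatment C203 samples (Weeks 12 to 104):

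- Base inclusion in the main descriptive row on days since the last recorded injection, within a window the sponsor prespecifies and justifies. An example is 14 ± 3 days, borrowed from the visit window.
- Require sampling before that day's dose only at visits with a dose. Week 104 has none, since the last dose is at Week 102.
- Leave Week 0 outside the rule, because those samples follow parent-study placebo and four-weekly arms for which 14 days is not the reference.
- Show an all-samples row alongside, so that late- and missed-dose levels stay visible for the compliance purpose in Protocol 3.3.6.

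In Listing 16.2.4.2, add date and time of last dose and days since last dose.

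The cost is SAP wording and one derived variable. Sampling times, last-dose dates and injection-card entries are already collected (Protocol 3.3.6 and 3.4.3.1). The downside is that some samples taken on the planned date leave the main row.

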## 9 ANALYSIS OF IMMUNOGENICITY

### 9.1 Available parameters

[figure not shown]
Immunogenicity is assessed via a tiered sample analysis approach (illustrated in Figure 1). In a first step all samples will be analyzed in the conventional anti-drug antibody (ADA) assay and only samples from subjects classified as 'Pre-Ab Pos – Equivocal' will be further analyzed in the mADA assay. This assay is a characterization assay and has been developed to enable detection of TE ADA in presence of (high) pre-existing antibody (pre-Ab) levels. Furthermore, positive ADA samples will be evaluated for their neutralizing potential in the neutralizing antibody (NAb) assay.

As such, the available parameters per sample are:

- ADA log10(titer) (no data imputation)
- mADA log10(titer) (for subset of subjects only, no data imputation)
- NAb normalized response (for subset of samples only, data imputation required for ADA negative samples)

Additional provided information needed for data interpretation is:

- ADA Minimum Significance Ratio (MSR): MSR is an assay parameter reflecting precision of titer assessments and is needed to interpret the treatment emergent (TE) response for subjects presenting with pre-Ab. In such cases, pre- and post-dose titers will be compared. The titer is considered to be significantly increased post-dose, if the highest post-dose titer compared to the highest pre-dose titer is higher than the MSR value. The increase of the log10(titer) post- versus pre-dose should be  $> \log_{10}(\text{MSR})$ .
- mADA MSR: MSR value determined in the mADA assay, similar application as described above, but applied to mADA titers.
- NAb assay cutpoint (CP): cut-off value to determine if a sample is negative or positive. Since the NAb assay is an inhibition assay, samples equal to or below the CP will be considered positive.

